APPENDIX 2. IMMUNE-RELATED RESPONSE EVALUATION CRITERIA IN SOLID TUMORS

Conventional response criteria may not be adequate to characterize the antitumor activity of immunotherapeutic agents, which can produce delayed responses that may be preceded by initial apparent radiographic progression, including the appearance of new lesions. Therefore, immunotherapy-specific response criteria adaptations to RECIST 1.1 ([Eisenhauer et al 2009](#)) have been developed to allow for unconventional response and progression patterns. These include modified RECIST 1.1 for immune-based therapeutics (iRECIST; [Seymour et al 2017](#)), which was developed by the RECIST working group in an effort to create a common set of criteria that the cancer immunotherapy field could apply to clinical trials.

Response evaluation through use of iRECIST requires collection of tumor assessment data after radiographic progression per RECIST 1.1. Details regarding lesion evaluation are described below. When not otherwise specified, RECIST 1.1 conventions will apply.

Criteria for determining overall response at a single time point per iRECIST are also summarized below. Of note, overall response per iRECIST will not be captured in the eCRF, but will instead be calculated programmatically by the Sponsor on the basis of Investigator-assessed individual lesion data recorded in the eCRF.

iRECIST response status is not a specific component of treatment discontinuation criteria, including decisions about whether to continue treatment beyond progression per RECIST 1.1. Investigators should instead take into account radiologic data and clinical status in making such decisions.

Evaluation of Lesions to Support IRECIST Response Assessment after Disease Progression per RECIST 1.1

iRECIST is an extension of RECIST 1.1 that allows for response assessment following disease progression per RECIST 1.1. RECIST 1.1 rules for categorizing lesions as measurable or nonmeasurable and measuring lesions (see [Appendix 1](#)) also apply to iRECIST. After disease progression per RECIST 1.1, the same target and nontarget lesions selected at baseline will continue to be followed, along with any new lesions that develop, to support iRECIST response evaluations, as described below and summarized in [Table 22](#). Once a lesion has been categorized as a target, nontarget, or new lesion, it will remain classified as such.

Target Lesions

The target lesions selected at baseline should continue to be measured at all tumor assessment time points after disease progression per RECIST 1.1, according to RECIST 1.1 conventions.

Nontarget Lesions

Nontarget lesions selected at baseline should continue to be followed at all tumor assessment time points after disease progression per RECIST 1.1. At each time point, nontarget lesions should continue to be categorized as “absent” (complete response [CR]), “unequivocal progression” relative to baseline (progressive disease [PD]), or “present without unequivocal progression” (non-CR/non-PD), as defined by RECIST 1.1. In addition, any nontarget lesions that were categorized as PD at the previous time point should be evaluated to determine whether there has been any further increase in size.

New Lesions

New lesions identified after baseline will be evaluated for measurability with use of the same criteria applied to prospective target lesions at baseline per RECIST 1.1 (e.g., nonlymph node lesions must be ≥ 10 mm on the longest diameter; new lymph nodes must be ≥ 15 mm on the short axis [see note below]). All new lesions (measurable or nonmeasurable) must be assessed and recorded at the time of identification and at all subsequent tumor assessment time points.

Up to a maximum of 5 measurable new lesions total (with a maximum of two lesions per organ) should be selected and measured at each time point. New lesions that are not measurable at first appearance but meet measurability criteria at a subsequent time point should be measured from that point on, if the maximum number of measurable new lesions has not been reached.

However, for calculation of the sum of diameters for new lesions, iRECIST excludes measurements from new lesions that were not measurable at first appearance.

All nonmeasurable new lesions (including those that subsequently become measurable) and additional measurable new lesions (in excess of 5 total or two per organ) should be assessed to determine whether there is any increase in size relative to the previous assessment time point.

Note regarding new lymph node lesions: If at first appearance the short axis of a lymph node lesion is ≥ 15 mm, it will be considered a measurable new lesion. If at first appearance the short axis of a lymph node lesion is ≥ 10 mm and < 15 mm, the lymph node will not be considered measurable but will still be considered a new lesion and should be identified as a nonmeasurable new lesion. If at first appearance the short axis of a lymph node is < 10 mm, the lymph node should not be considered pathological and should not be considered a new lesion. A lymph node can subsequently become measurable, when the short axis is ≥ 15 mm. Measurable new lymph node lesions should continue to be measured at all subsequent time points, even if the short axis decreases to < 15 mm (or even < 10 mm).

Table 22: Guidelines for Evaluation of Lesions to Support iRECIST Response Assessment after Disease Progression per RECIST 1.1

Lesion Type	Evaluation of Lesions to Support iRECIST Response Assessment after Disease Progression per RECIST 1.1
Target lesions	
Measurements should be continued according to RECIST 1.1 conventions.
Nontarget lesions	
Nontarget lesions should continue to be categorized as absent (CR), unequivocal progression (PD), or present without unequivocal progression (non-CR/non-PD), as defined by RECIST 1.1. In addition, any nontarget lesions that were categorized as PD at the previous time point should be evaluated to determine whether there has been any further increase in size.
New lesions	
New lesions should be evaluated for measurability per RECIST 1.1.All new lesions (measurable or nonmeasurable) must be assessed and recorded at the time of identification and at all subsequent tumor assessment time points.Up to a maximum of five measurable new lesions total (with a maximum of two lesions per organ) should be selected and measured at each time point.All nonmeasurable new lesions (including those that subsequently become measurable) and additional measurable new lesions (in excess of five total or two per organ) should be assessed to determine whether there is any increase in size relative to the previous assessment time point.

Abbreviations: CR = complete response; iRECIST = modified RECIST 1.1 for immune-based therapeutics; PD = progressive disease; RECIST 1.1 = Response Evaluation Criteria in Solid Tumors, Version 1.1

APPENDIX 3. LYMPHOMA RESPONSE TO IMMUNOMODULATORY THERAPY CRITERIA

Immunomodulatory agents may be associated with clinical and imaging findings during treatment that are suggestive of progressive disease despite evidence of clinical benefit (e.g., tumor flare or pseudo-progression). The response criteria outlined below, which have been adapted from the Lymphoma Response to Immunomodulatory Therapy Criteria (LYRIC) (Cheson et al 2016), should be implemented to assess disease status for patients with lymphoma who receive immunomodulatory agents.

Table 23: Guidelines for the Classification of Disease Status According to LYRIC

Complete Response	Partial Response	Progressive Disease

PET-CT score 1, 2, or 3* with or without a residual mass on 5PS†
 
OR
 
On CT, target nodes/nodal masses must regress to ≤ 1.5 cm in LDi.
	
PET-CT score 4 or 5 with reduced uptake compared with baseline and residual mass(es) of any size.
 
OR
 
On CT, $\geq 50\%$ decrease in SPD of up to 6 target measurable nodes and extranodal sites.
	
PET-CT score 4 or 5 with an increase in intensity of uptake from baseline and/or new FDG-avid foci consistent with lymphoma at interim or end-of-treatment assessment.
 
OR
 
On CT, an individual node/lesion must be abnormal with:
 
 LDi > 1.5 cm and increase by $\geq 50\%$ from PPD nadir and an increase in LDi or SDi from nadir 0.5 cm for lesions > 2 cm 1.0 cm for lesions > 2 cm 
In the setting of splenomegaly, the splenic length must increase by $> 50\%$ of the extent of its prior increase beyond baseline (e.g., a 15-cm spleen must increase to > 16 cm). If no prior splenomegaly, must increase by ≥ 2 cm from baseline. New or recurrent splenomegaly
 
New or clear progression of pre-existing nonmeasured lesions
 
Regrowth of previously resolved lesions
 
A new node > 1.5 cm in any axis or a new extranodal site > 1.0 cm in any axis; if < 1.0 cm in any axis, its presence must be unequivocal and must be attributable to lymphoma
 
Assessable disease of any size unequivocally attributable to lymphoma
 
AND/OR new or recurrent involvement of the bone marrow
 
The above criteria apply with the following exceptions for IR:
 
IR(1): $\geq 50\%$ increase in SPD in first 12 weeks of therapy
 
IR(2): $< 50\%$ increase in SPD with
 
 a. New lesion(s), or b. $\geq 50\%$ increase in PPD of a lesion or set of lesions at any time during treatment 
IR(3): Increase in FDG uptake without a concomitant increase in lesion size or number meeting criteria for PD

Abbreviations: CT = computed tomography; FDG = fluorodeoxyglucose; IR = immune response; LDi = longest diameter; PET = positron emission tomography; PPD = product of the perpendicular diameters; SDi = short diameter; SPD = sum of the product of diameters; 5PS = 5-point scale.

*A score of 3 in many patients indicates a good prognosis with standard treatment, especially if at the time of an interim scan. However, in trials involving PET where de-escalation is investigated, it may be preferable to consider a score of 3 as inadequate response (to avoid undertreatment).

†PET 5PS: 1 = no uptake above background; 2 = uptake \leq mediastinum; 3 = uptake $>$ mediastinum but \leq liver; 4 = uptake greater than liver; 5 = uptake markedly higher than liver (2-3 times SUVmax in normal liver) and/or new lesions; X = new areas of uptake unlikely to be related to lymphoma.

The term “immune response” (IR) does not make direct reference to the underlying mechanism, recognizing that a delayed response and an immune-mediated flare can both occur in the early treatment period and may be difficult to distinguish from progression by physical examination or imaging alone. Moreover, the term provides the flexibility to allow patients to continue treatment past IR in some circumstances with a subsequent evaluation within 12 weeks to confirm or refute true progressive disease. A patient will be considered to have IR in 1 or more of the 3 following circumstances.

1. **Increase in overall tumor burden (as assessed by sum of the product of the diameters [SPD]) of $\geq 50\%$ of up to 6 measurable lesions in the first 12 weeks of therapy, without clinical deterioration [IR(1)].** This pattern may be seen as a consequence of either delayed response or early immune-mediated flare. At least within the context of clinical trials, a biopsy is encouraged in this case because this may help to distinguish the two and, if positive, will confirm the impression of progressive disease. However, if negative for lymphoma, it will support the concept of pseudo-progression and contribute to our understanding of this phenomenon. When such a biopsy is neither safe nor feasible, decisions should be based on a repeat scan 12 weeks after the initial determination of IR.

It is recognized that “clinical deterioration” is subjective. In some cases, the simple growth of a nodal or tumor mass could worsen the symptoms mechanically related to that mass, such as pain at the tumor site, compression of adjacent structures, etc. Such an increase in symptoms that can be directly attributed to the size of the tumor mass may not be considered as clinical deterioration in this context. However, in most cases, patients should be experiencing clinical stability or improvement by Investigator assessment to be considered as having IR, and in all cases, the patient must be considered likely to tolerate continued treatment and not at risk of serious complications should further tumor growth occur.

2. **Appearance of new lesions or growth of one or more existing lesion(s) $\geq 50\%$ at any time during treatment; occurring in the context of lack of overall progression (< 50% increase) of overall tumor burden, as measured by SPD of up to 6 lesions at any time during the treatment [IR(2)].** This phenomenon may occur early or late in the treatment course, and therefore, unlike IR(1), is not defined by its temporal relationship to treatment initiation. Both within and outside the context of clinical trials, a biopsy is strongly encouraged in such cases. If the biopsy does not confirm the presence of viable tumor in the new or enlarging lesion(s), then the lesion(s) are not considered active disease and should not be used in subsequent SPD assessments.
3. **Increase in FDG uptake of 1 or more lesion(s) without a concomitant increase in lesion size or number [IR(3)].** Increased immune activity at the site of tumor may manifest as an increase in FDG uptake. Therefore, by itself, changes in uptake should not trigger an assignment of progressive disease with checkpoint inhibitors. The magnitude of increase in uptake in an immune-mediated flare compared with that in true tumor progression is not yet known. It is important to investigate this finding, especially in conjunction with biopsies of the lesion in question.

An increase in FDG avidity of 1 or more lesions suggestive of lymphoma, without a concomitant increase in size of those lesions meeting progressive disease criteria does not constitute progressive disease.

It is possible that, at a single time point, a patient could fulfill criteria for both IR(1) or IR(2) and IR(3): for example, there could be a new FDG avid lesion in the absence of overall progression [IR(2)], and, at the same time, increase in FDG uptake of a separate lesion [IR(3)]. In such cases, the designation of IR(1 or 2) should take priority [e.g., IR(2)] in the above example.

In patients categorized as having any of the above types of IR, repeat imaging should be obtained after an additional 12 weeks (or earlier if clinically indicated). At that time, response should be re-evaluated, and the patient should be considered to have true progressive disease if the SPD of target lesion has increased further, with the considerations below:

- In the case of IR(1), the comparison should be between the first IR(1) and the current SPD, with an increase of $\geq 10\%$ constituting progressive disease. In addition, there should be an increase of ≥ 5 mm (in either dimension) of ≥ 1 lesion for lesions ≤ 2 cm and 10 mm for lesions > 2 cm. The 10% threshold is empiric but designed to account for variability in measurement, especially when taken along with the minimum increase. If the target SPD increase is $< 10\%$, the response would still be categorized as IR(1), and the patient could continue treatment until a subsequent scan shows either true progressive disease [$\geq 10\%$ increase from first IR(1) time point and an increase of > 5 mm in either dimension of ≥ 1 lesion] or response ($\geq 50\%$ decrease from baseline). In this situation, it is reasonable to repeat imaging in 4 to 8 weeks of the original IR(1) time point to ensure absence of significant further increase.
- In the case of IR(2), the new or growing lesion(s) (unless biopsy proven to be benign) should be added to the target lesion(s), up to a total of no more than 6 total lesions. If the SPD of the newly defined set of target lesions has increased $\geq 50\%$ from their nadir value (which may precede the IR time point), the patient should be considered to have progressive disease.
- In the case of IR(3), because inflammatory responses may result in an increase in the standardized uptake value of a lesion, the patient will not be considered to have PD unless there is evidence of PD by an increase in lesion size or the development of new lesions, as noted above.

Importantly, if a patient is assessed as having IR and then “true” progressive disease at a subsequent time point (without an intervening objective response between IR and progressive disease), the IR assessment should subsequently be corrected to progressive disease for reporting purposes to the date of the prior designation of IR. While these lesions may remain stable during the time of observation, the initial designation of IR should be changed to progressive disease.

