APPENDIX 1. RESPONSE EVALUATION CRITERIA IN SOLID TUMORS, VERSION 1.1

The following immune-related response criteria, adapted from the RECIST, version 1.1, guidelines ([Eisenhauer et al 2009](#)), should be implemented to assess disease status for patients with solid tumors.

Tumor Measurability

At baseline, tumor lesions/lymph nodes will be categorized as measurable or nonmeasurable as described below. All measurable and nonmeasurable lesions should be assessed at screening and at subsequent protocol-specified tumor assessment time points. Additional assessments may be performed as clinically indicated for suspicion of progression.

Definition of Measurable Lesions

Tumor Lesions

Tumor lesions must be accurately measured in at least one dimension (longest diameter in the plane of measurement is to be recorded) with a minimum size as follows:

- 10 mm by computed tomography (CT) or magnetic resonance imaging (MRI) scan (CT/MRI scan slice thickness/interval ≤ 5 mm)
- 10-mm caliper measurement by clinical examination (lesions that cannot be accurately measured with calipers should be recorded as nonmeasurable)
- 20 mm by chest X-ray

Malignant Lymph Nodes

To be considered pathologically enlarged and measurable, a lymph node must be ≥ 15 mm in the short axis when assessed by CT scan (CT scan slice thickness recommended to be ≤ 5 mm). At baseline and follow-up, only the short axis will be measured and followed. Additional information on lymph node measurement is provided below (see “Identification of Target and Nontarget Lesions” and “Calculation of Sum of Diameters”).

Definition of Nonmeasurable Lesions

Nonmeasurable tumor lesions encompass small lesions (longest diameter < 10 mm or pathological lymph nodes with short axis ≥ 10 mm but ≤ 15 mm) as well as truly nonmeasurable lesions. Lesions considered truly nonmeasurable include leptomeningeal disease, ascites, pleural or pericardial effusion, inflammatory breast disease, lymphangitic involvement of skin or lung, peritoneal spread, and abdominal mass/abdominal organomegaly identified by physical examination that is not measurable by reproducible imaging techniques.

Special Considerations Regarding Lesion Measurability

Bone lesions, cystic lesions, and lesions previously treated with local therapy require particular comment, as outlined below.

Bone Lesions:

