To reiterate, however, if the radiologist is able to provide an actual measurement, that should be recorded, even if it is $< 5\text{ mm}$, and in that case “too small to measure” should not be ticked.

Measuring Lesions That Split or Coalesce on Treatment

When nonlymph node lesions fragment, the longest diameters of the fragmented portions should be added together to calculate the sum of diameters. Similarly, as lesions coalesce, a plane between them may be maintained that would aid in obtaining maximal diameter measurements of each individual lesion. If the lesions have truly coalesced such that they are no longer separable, the vector of the longest diameter in this instance should be the maximum longest diameter for the coalesced lesion.

Evaluation of Nontarget Lesions

Measurements are not required for nontarget lesions, except that malignant lymph node nontarget lesions should be monitored for reduction to < 10 mm in short axis. Nontarget lesions should be noted at baseline and should be identified as “present” or “absent” and (in rare cases) may be noted as “indicative of progression” at subsequent evaluations. In addition, if a lymph node lesion shrinks to a nonmalignant size (short axis < 10 mm), this should be captured on the eCRF as part of the assessment of nontarget lesions.

Response Criteria

Criteria for Target Lesions

Definitions of the criteria used to determine objective tumor response for target lesions are provided below:

- Complete response (CR): Disappearance of all target lesions
 - Any pathological lymph nodes must have reduction in short axis to < 10 mm.
- Partial response (PR): At least a 30% decrease in the sum of diameters of all target lesions, taking as reference the baseline sum of diameters, in the absence of CR
- Progressive disease (PD): At least a 20% increase in the sum of diameters of target lesions, taking as reference the smallest sum of diameters at prior time points (including baseline)
 - In addition to the relative increase of 20%, the sum of diameters must also demonstrate an absolute increase of ≥ 5 mm.
- Stable disease (SD): Neither sufficient shrinkage to qualify for CR or PR nor sufficient increase to qualify for PD

Criteria for Nontarget Lesions

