Patients’ best overall response will be selected based on the overall response order (CR, PR, SD, PD, NE for RECIST; CR, PR, SD, PD, IR1, IR2, IR3 for LYRIC) through the study. Objective Response Rate (ORR), defined as the proportion of patients’ overall response achieving a PR or CR at any time on the study, will be summarized descriptively by arm and cohort. In addition, an exact 90% confidence interval (CI) will be presented for RP2D cohort in Arm 2. Note that the definition of the Efficacy Population includes all treated patients who have an on-treatment response assessment or who discontinued study early due to disease progression; therefore, all Efficacy Population patients will be included in the denominators for percentage even if the patient had a Not Evaluable response. The best overall response and objective response rate will be summarized separately for each assessment method (RECIST, iRECIST, or LYRIC).

Similarly, the proportion of patients with a PR and the proportion of patients with a CR at any time during the study will be summarized as part of the best

overall response. The sum of diameters and change from baseline will also be summarized, by arm and cohort at each assessment visit.

All overall tumor and lymphoma response data will be presented in patient listings.

3. Determination of Time to Event Endpoints

Below is a list of events definitions for the solid tumor patients with a confirmed response according to RECIST v1.1 and iRECIST, and lymphoma patients with response according to LYRIC. The number of events and the number of censored patients will be summarized. The median time to event (reported in days) and the 25th and 75th percentiles on the time to event for each arm and cohort will be summarized using Kaplan-Meier estimates. Progression-Free Survival graphs will also be provided.

When calculating the endpoint that involve PD diagnosis date, such as time to progression or progression free survival, below rules will apply to account for the repeated PD response assessment per iRECIST:

- When a patient has disease progression per RECIST, if the repeated assessment confirmed as disease progression according to iRECIST criteria, the first PD date will be used in the endpoint calculation.

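### In Table 23 the CT rule for lymphoma complete response covers fewer lesions than the rule for partial response, so unchanged extranodal disease can be scored CR

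*Protocol*

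**What the plan says.** Protocol Appendix 3 introduces its adapted lymphoma criteria as ones that "should be implemented to assess disease status for patients with lymphoma who receive immunomodulatory agents". Table 23 then gives a PET-CT route and a CT route to each category, joined by OR.

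- **CR, CT route:** "target nodes/nodal masses must regress to" 1.5 cm or less in LDi. The cell says nothing about extranodal target lesions or nonmeasured disease.
- **PR, CT route:** at least a 50% "decrease in SPD of up to 6 target measurable nodes and extranodal sites".
- **PD, CT route:** growth of individual nodes or lesions, splenic enlargement, new or progressing nonmeasured lesions, and new disease, including "a new extranodal site > 1.0 cm in any axis".

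SAP VII.A.1 lists a complete radiologic response among the CT categories but does not define it. It also lists a Combined Overall Response, without saying how the CT and PET-CT results are merged. SAP VII.A.2 calculates SPD over all target lesions, puts CR first in the order for best overall response, and takes ORR as "defined as the proportion of patients’ overall response achieving a PR or CR at any time on the study". ORR is a secondary objective (Protocol Section 3.2).

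**The concern.** A better response category should be at least as hard to reach as a lesser one. Here CR is judged on a subset of the lesions that PR is judged on, so a time point can satisfy the better category and fail the lesser one. Extranodal lymphoma is foreseeable in this trial: inclusion criterion 5 admits non-nodal lesions of 10 mm or more and allows liver injection.

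At stake is the LYRIC response table. A patient with persisting, unchanged extranodal lymphoma could be recorded as a complete responder. In some cases that patient would enter the ORR numerator without having met any other response rule on CT.

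**Working it through.** The documents give no figure on this point to reproduce. The check applies the two CT cells literally to lesion sizes that are **assumed for illustration**.

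**Rules applied.** CR: every target node has LDi ≤ 1.5 cm. PR: SPD over nodes plus extranodal sites falls by at least 50%.

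**Example 1: extranodal disease dominates.** The node goes from 2.0 × 1.5 cm to 1.4 × 1.0 cm; the extranodal lesion stays at 4.0 × 4.0 cm.
- Baseline SPD = 2.0 × 1.5 + 4.0 × 4.0 = 3.0 + 16.0 = 19.0 cm²
- Follow-up SPD = 1.4 × 1.0 + 4.0 × 4.0 = 1.4 + 16.0 = 17.4 cm²
- Change = (17.4 − 19.0)/19.0 = −8.4%
- CT CR: met (1.4 cm ≤ 1.5 cm). CT PR: not met.

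**Example 2: nodes dominate.** The node goes from 40 × 30 mm to 14 × 10 mm; the extranodal lesion stays at 15 × 10 mm.
- Baseline SPD = 1200 + 150 = 1350 mm²; follow-up SPD = 140 + 150 = 290 mm²
- Change = (290 − 1350)/1350 = −78.5%
- CT CR: met. CT PR: met. The patient is a responder either way, so the error is CR in place of PR.

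**Where the line falls.** Let f be the extranodal share of baseline SPD, unchanged at follow-up, and r the proportional fall in nodal SPD. The total fall is (1 − f) × r, so PR fails when f > 1 − 0.5/r:

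| Fall in nodal SPD, r | PR fails when f exceeds |
|---|---|
| 65% | 0.23 |
| 80% | 0.375 |
| 90% | 0.44 |
| 100% | 0.50 |

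If unchanged extranodal disease is more than half of baseline SPD, PR always fails, yet CT CR is met once the nodes are at 1.5 cm or less.

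**Does other text close the gap?**
- The Appendix 1 requirement, "Disappearance of all target lesions", belongs to criteria that "should be implemented to assess disease status for patients with solid tumors". It does not govern lymphoma.
- The PD column catches growth and new sites. A baseline extranodal lesion that has not changed is neither.
- One PD-column line, "Assessable disease of any size unequivocally attributable to lymphoma", directly follows the new-lesion line and is not a condition on CR. Read in isolation it would label the same patient PD, which adds a contradiction and does not repair the CR cell.

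**New lesions and PR.** A 50% fall in SPD together with a new lesion meets the PR cell. It also meets IR(2), because the SPD increase is below 50%. Table 23 does not say which takes precedence, and the SAP order places PR ahead of IR2.

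**If CT CR also required extranodal resolution,** Example 1 would be neither CR nor PR and would leave the ORR numerator. Example 2 would become PR and stay in it.

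**The case against.** The strongest reply is that Table 23 is a summary. It is headed as guidelines and adapted from a cited publication, and SAP VII.A.1 cites that publication directly and does not point to Appendix 3. Response is judged by the local Investigator (Protocol Section 7.3), who would see an unshrunk lesion. SPD over all target lesions and the injected lesion's measurements are also reported, so the discrepancy would be visible. These points moderate the practical risk. They do not remove the defect: Appendix 3 directs that its criteria be implemented, the CR cell reads as a complete rule, and neither document says that something else overrides it.

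Several stronger readings are tempting but not supported:

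- **That CT CR overrides a PET-CT score of 4 or 5.** The SAP assesses CT and PET-CT separately and then assigns a Combined Overall Response. The combining rule is missing, so precedence for CT is not established. A score of 4 or 5 with reduced uptake would also meet the PET-CT route to PR, so the failure of PR shown here concerns the CT branch only.
- **That new lesions are ignored.** The PD column covers new nodes, new extranodal sites, new or progressing nonmeasured lesions and new or recurrent splenomegaly, and SAP VII.A.2 treats new malignant lesions as progression. What is uncovered is persisting baseline disease, together with the unstated precedence when PR and a new-lesion criterion coincide.
- **That duration of response is overstated.** Adding misclassified responders could lengthen or shorten it; the documents do not settle the direction.
- **That a patient with no target node is automatically CR.** This follows only from a strictly literal reading, since requiring nodes to regress presupposes that there are some. The point does not depend on it.

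**Conclusion.** The point holds for the CT branch of Table 23. With regressed nodes and unchanged baseline extranodal disease, the CT criterion for CR is met; the CT criterion for PR fails when extranodal disease is a large enough share of the burden. Where nodes dominate, CR replaces PR and ORR does not move. The rule as written can therefore misclassify LYRIC best overall response and, in part of the cases, inflate LYRIC ORR.

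The lesion sizes above are assumptions and show only that the conflict occurs. A reader might turn one such patient into a shift in ORR for a 20-patient group or a 3-patient cohort. The documents do not support that: LYRIC results are summarized separately and the number of lymphoma patients is not given, so the effect cannot be sized.

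The endpoint is secondary and descriptive, and the primary DLT endpoint is untouched. The error should still be corrected before analysis, since it concerns a stated rule that yields a wrong category.

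**What to change.** 1. **Protocol Table 23, CT CR cell:** in addition to the nodal condition, require resolution of baseline extranodal target sites and no residual nonmeasured lymphoma, so that CR covers at least the lesions counted for PR.
2. **Same table:** state that a time point meeting a new-lesion criterion for PD or IR cannot be scored CR or PR.
3. **SAP VII.A.1:** carry the same definition, and give the rule for combining CT and PET-CT into the Combined Overall Response.

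The cost is a short edit to the table and matching text in the SAP, with no new imaging or data collection. The downside is that LYRIC CR counts may be slightly lower.

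### The CT progression rule for lymphoma in Protocol Appendix 3, Table 23, gives lesions above 2 cm two minimum-growth cut-offs and lesions above 1.5 cm up to 2 cm none

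*Protocol*

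**What the plan says.** Protocol Appendix 3 is more than background. Its criteria "should be implemented to assess disease status for patients with lymphoma who receive immunomodulatory agents".

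On CT, the Progressive Disease column of Table 23 asks for three things together in an individual node or lesion: a longest diameter (LDi) above 1.5 cm, a rise of at least 50% in the product of perpendicular diameters (PPD) from nadir, "and an increase in LDi or SDi from nadir". Two lines then give the size of that last increase: "0.5 cm for lesions > 2 cm" and "1.0 cm for lesions > 2 cm".

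Later in Appendix 3, the rule for confirming progression after IR(1) asks for at least 5 mm of growth in at least one "lesion for lesions ≤ 2 cm and 10 mm for lesions > 2 cm". The bracket that closes the same bullet mentions only growth of more than 5 mm, with no split by size.

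The SAP does not restate or correct these thresholds. Section VII.A.1 lists the LYRIC response categories, and Appendix 5 plans tables of time to progression (TTP), progression-free survival (PFS) and duration of response (DOR) by LYRIC.

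A smaller boundary slip sits in Appendix 1. A node of 15 mm or more in short axis is measurable, yet the nonmeasurable class takes in "pathological lymph nodes with short axis" from 10 mm up to and including 15 mm. The paragraph on target and nontarget nodes repeats that range. Appendix 2 stops the range below 15 mm: in it, "the lymph node will not be considered measurable but will still be considered a new lesion".

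**The concern.** Both Table 23 lines carry the same size condition, so a lesion above 2 cm that has grown by between 0.5 and 1.0 cm meets one line and fails the other. A lesion above 1.5 cm but not above 2 cm can enter the rule through the first two conditions and then finds no absolute minimum.

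Local investigators at about 8 centers assess response (Protocol synopsis and Section 7.3), so sites could resolve the conflict differently. The date of progression by LYRIC feeds TTP, PFS and, in responders, DOR. Progression also ends eligibility for further cycles (Protocol Section 4.2.1), so the ambiguity can reach a treatment decision where CT-based progression is called.

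**Working it through.** There is no plan figure to reproduce, so the check compares the texts and then does simple arithmetic. The lesion sizes are assumptions for illustration; the documents give none.

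**1. The rules side by side**

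| Lesion size | Table 23 as printed | IR(1) rule, main sentence | IR(1) rule, closing bracket |
|---|---|---|---|
| Above 1.5 cm, up to 2 cm | no minimum | 5 mm | more than 5 mm |
| Above 2 cm | 0.5 cm and 1.0 cm | 10 mm | more than 5 mm |

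On any reading of Table 23 one line is idle. If both must be met, the 0.5 cm line does nothing. If either is enough, the 1.0 cm line does nothing.

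**2. A lesion above 2 cm.** Take PPD = LDi × SDi, with SDi the short diameter, and growth = the larger of the increases in LDi and SDi.
- Nadir 2.5 × 2.0 cm: PPD = 5.00. Current 3.2 × 2.4 cm: PPD = 7.68.
- Change: 7.68 / 5.00 − 1 = +53.6%. Growth: 3.2 − 2.5 = 0.7 cm.
- The first two conditions are met. Growth of 0.7 cm passes the 0.5 cm line and fails the 1.0 cm line, so the result is undetermined.

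**3. A lesion not above 2 cm**
- Nadir 1.4 × 1.0 cm: PPD = 1.40. Current 1.8 × 1.2 cm: PPD = 2.16.
- Change: 2.16 / 1.40 − 1 = +54.3%. Growth: 1.8 − 1.4 = 0.4 cm.
- LDi exceeds 1.5 cm and the relative rise is met. As printed, no absolute minimum applies. Under a 5 mm minimum, 0.4 cm would fall short.

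**4. The range of sizes affected.** For a round lesion whose PPD grows by exactly 50%, the diameter grows by √1.5 − 1 = 0.22474 of its nadir value.
- Growth reaches 0.5 cm at a nadir of 0.5 / 0.22474 = 2.225 cm.
- Growth reaches 1.0 cm at a nadir of 1.0 / 0.22474 = 4.449 cm.
- Between these, roughly 2.2 to 4.4 cm, the two printed lines disagree.
- At a nadir of 2 cm or less, growth is at most 0.22474 × 2 = 0.449 cm. A 5 mm minimum, had one been printed, would not be met there.

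**5. Which patients reach these lines.** Table 23 makes exceptions for immune response (IR). IR(1) covers a rise of at least 50% in the summed products (SPD) in the first 12 weeks, without clinical deterioration. IR(2) covers growth of single lesions, or new lesions, with an SPD rise below 50%, at any time. That leaves mainly an SPD rise of at least 50% after week 12, or one with clinical deterioration. Inclusion criterion 5 requires only one measurable lesion. With a single target lesion SPD equals PPD, so after week 12 a rise of at least 50% falls outside both exceptions and the faulty lines decide.

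**The case against.** The strongest reply is that the lines seldom decide anything. Table 23 also has a PET-CT route, and CT progression can be called on other grounds such as new or regrowing lesions or the spleen. The IR exceptions remove much early growth, and confirmation after IR(1) or IR(2) follows its own rules. All of this stands and limits the reach of the point. It does not remove the case in step 5.

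Four wider readings are tempting, and the documents do not support them.

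- **Objective response rate.** SAP Section VII.A.2 counts a partial or complete response at any time, and those columns of Table 23 do not use these lines. Any effect would be indirect, through stopping treatment early.
- **Continuation past Cycle 4 in general.** Four 21-day cycles are 84 days, or 12 weeks, so an on-schedule scan at the end of Cycle 4 falls at the edge of the IR(1) window. Appendix 3 also allows treatment past IR.
- **Eligibility.** Inclusion criterion 5 itself sets 15 mm or more for nodes. The Appendix 1 overlap touches only the labelling of a node of exactly 15 mm.
- **A wrong value programmed in the SAP.** No programmed LYRIC derivation is described. Protocol Appendix 2 states programming by the sponsor for iRECIST only.

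A sign lost in text conversion from PDF is also possible. It is unlikely, because the less-than-or-equal sign appears correctly in the complete-response cell of the same table and in the IR(1) rule, but the source should be checked. Nor is the IR(1) rule a perfect anchor: it serves a different test, and its closing bracket drops the size split.

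**Conclusion.** The inconsistency is real. As printed, Table 23 gives no determinate CT answer for a lesion above 2 cm that meets the relative criterion with growth of at least 0.5 cm but under 1.0 cm. It sets no absolute minimum for lesions above 1.5 cm up to 2 cm, although the LDi and 50% PPD conditions still apply to them. It bears on TTP, PFS and responders' DOR by LYRIC, and on continuation where CT progression is called.

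It is a minor to moderate correction. The efficacy analyses are descriptive, TTP, PFS and DOR sit under exploratory objectives, and the primary DLT endpoint does not use these criteria. A reader might infer that every lymphoma patient's result is in doubt; the PET-CT route and the IR exceptions rule that out. The number of lymphoma patients is not stated, so the count affected cannot be given. The 2.2 to 4.4 cm range assumes a round lesion and exactly 50% growth in PPD; other shapes and larger growth shift it.

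**What to change.** Check the source PDF and the cited LYRIC criteria. Then reconcile the Progressive Disease column of Table 23 with the IR(1) confirmation rule, including that rule's closing bracket, so that each size class has exactly one minimum-growth cut-off. Which value belongs to which class is for the sponsor to settle from the cited criteria, since progression also governs continuation of treatment. Apply the reconciled rule in all LYRIC assessments and in the SAP summaries of TTP, PFS and DOR.

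As a minor tidy-up, reconcile the 10 to 15 mm nodal range in Appendix 1, in both places, with its own measurability rule and with Appendix 2.

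The cost is a few characters in an administrative amendment and a note to sites. If LYRIC assessments have already been made, the CT progression calls that rest only on growth of an existing lesion should be looked at again.
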